**cohort/dose level -1 (100mg days 0 and 14) will be pursued only if 2/3 patients in cohort 1 (300mg days 0 and 14) experience DLT.*

Phase I trial endpoint:

Safety of escalating dose of ofatumumab in combination with prednisone.

Definition of dose-limiting toxicity (DLT):

Dose-limiting toxicity attributable to ofatumumab within 46 days of initiation of ofatumumab therapy is defined in the *above section V.1 safety for definition of DLT*. The occurrence of DLT attributable to ofatumumab in $\leq 17\%$ serves as the boundary for the maximally tolerated dose (MTD) of ofatumumab.

Phase I trial procedures and analysis:

The initial group of 3 patients will be enrolled in the cohort 1. Dose escalation of ofatumumab will proceed according to the following: If no DLT is observed among 3 patients in a cohort, the next group of 3 will be treated at the next highest dose level. If the current level (i.e., the level at which no DLTs are observed) is the highest dose

level, three additional patients will be enrolled (total of six). If one DLT is observed among 3 patients in a cohort, the next group of 3 will be treated at this same dose level. If no more DLT is observed among the 3 additional patients (i.e. one DLT in total is observed among the 6 patients), then the next 3 patients will be treatment at the next highest dose level. If at least 1 more DLT is observed among the 3 additional patients, then the MTD is exceeded. If 6 patients have been treated at the next lower dose level, it will be considered as the MTD. If not, three additional patients will be enrolled. This escalation approach will then be continued until a dose is identified where at most 1 of 6 patients has a DLT. That dose will be considered to be the MTD. If two DLTs are observed among 3 (or fewer) patients in a cohort, the next group of 3 will be treated at the next lowest dose level. If the current level (i.e. the level at which 2 DLTs are observed) is the lowest dose level (300mg days 0 and 14), then a dose level -1 will be pursued, in which a de-escalated dose of 100mg ofatumumab will be given on days 0 and 14.

The total number treated on the phase I component will depend on the occurrence of dose limiting toxicity (DLT), however the maximal number accrued on the phase I study would approximate 12 to 18 total subjects. GSK reviewed phase I data prior to moving forward with the phase II component.

Phase II component:

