An early stopping rule for toxicity is constructed to continuously monitor the rate of DLT (i.e. grade 4 AE attributable to ofatumumab per the above definitions) for the 38 patients in a Phase II component. The DLT is defined in Section V.1. Safety. The stopping boundaries for monitoring the DLT is constructed as a Pocock-type boundary as described in “Continuous Toxicity Monitoring in Phase II Trials in Oncology” by Ivanova, Qaqish, and Schell (Biometrics, 2005; 61(2):540-45). Table below shows the number of DLTs allowed for a given number of “assessable” patients up to that point. Patients are considered to be “assessable” when they have either experienced a DLT or completed the surveillance period (death without a DLT or 30 days after infusion of Ofatumumab) without having experienced a DLT so that their outcomes are identifiable. Up to 20% of DLT rate is expected or acceptable. The table below contains the stopping boundaries for toxicity, based on which the probability of early stopping is at most 0.05 if the DLT rate is equal to 6.5%. Given the first 6 patients on the phase II component were treated on the phase I component of the trial (and assessed for DLT in the phase I component), the starting number of sequentially enrolled patients for assessment of this toxicity stopping boundary in the phase II component of the trial has been modified (see below table). When the DLT rate is unacceptably high (30%), the stopping rule has greater than 97% probability of early stopping. If a stopping boundary is reached, the accrual will be halted, and the data will be reviewed by the Moffitt Cancer Center Protocol Monitoring Committee.

# Assessable	Stopping boundaries for DLT	# Assessable	Stopping boundaries for DLT
1	NA	20	5
2	NA	21	5
3	NA	22	5
4	NA	23	5
5	NA	24	5
6	NA	25	5
7	NA	26	6
8	3	27	6
9	3	28	6
10	3	29	6
11	3	30	6
12	4	31	6
13	4	32	6
14	4	33	7
15	4	34	7
16	4	35	7
17	4	36	7
18	4	37	7
19	5	38	7

* These stopping boundaries apply to both the MTD cohort patients from the phase I component that move forward to the phase II trial, as well as those patients enrolled initially in the phase II component of the trial

* If these stopping boundaries are met, accrual will be suspended and the data will be reviewed in detail by the Protocol Monitoring Committee (PMC). The study will not be terminated, however. Resumption of accrual will be dictated by the review of the data by the study investigators and the PMC.

VII. DATA AND SAFETY MONITORING:

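### The two stated probabilities for the toxicity stopping rule describe 38 unselected patients; given the 0 or 1 DLT that the phase I cohort must have, the phase II rule does not have both properties

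*Combined protocol and SAP*

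**What the plan says.** Section VI, Early Stopping Rule for Toxicity, sets up continuous monitoring of DLTs "for the 38 patients in a Phase II component", with a Pocock-type boundary. The table has no boundary for assessable patients 1 to 7. It then prints 3 (patients 8–11), 4 (12–18), 5 (19–25), 6 (26–32) and 7 (33–38).

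Two operating characteristics are given. At the low rate, "the probability of early stopping is at most 0.05 if the DLT rate is equal to 6.5" per cent. At the high rate, "When the DLT rate is unacceptably high (30%), the stopping rule has greater than 97% probability of early stopping".

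The section acknowledges the phase I carry-over: "Given the first 6 patients on the phase II component were treated on the phase I component of the trial". It says the starting number was modified for that reason, and a footnote confirms that the carried-forward patients count: "These stopping boundaries apply to both the MTD cohort patients from the phase I component that move forward to the phase II trial".

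Section VI, Phase I trial procedures and analysis, continues escalation "until a dose is identified where at most 1 of 6 patients has a DLT" and calls that dose the MTD. Section VI, Phase II component, adds 32 new patients to those six to make 38.

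**The concern.** The rule does not run on 38 fresh patients. It starts at patient 6, and those six were selected for low toxicity: a cohort with two or more DLTs would not have defined the MTD, and phase II would not have opened at that dose. Starting the looks at patient 8 changes when monitoring begins but does not undo the selection. The stated probabilities are therefore not those of the rule as it will operate, and no figures conditional on the phase I result are given.

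At stake is what the Protocol Monitoring Committee and the investigators may assume about the rule. After a clean phase I cohort it is less sensitive than stated to a rate the plan calls unacceptably high. After one phase I DLT it pauses accrual more often than stated at the low rate.

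**Working it through.** **Inputs, all from Section VI.** Boundaries b(n) as printed, for n = 8 to 38; DLT rates p = 6.5% and 30%; six patients carried forward with 0 or 1 DLT; 32 new patients. Assumptions: DLTs are independent with a common rate, there is a look at every assessable patient, and a halt occurs when the cumulative count reaches b(n).

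**Method.** Let f(n, k) be the probability of having k DLTs after n patients with no halt so far. Then

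f(n, k) = f(n−1, k)·(1−p) + f(n−1, k−1)·p,

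and at each n ≥ 8 the probability at k ≥ b(n) is moved to the halted total. Only the starting state differs: f(0, 0) = 1 for unselected patients, f(6, 0) = 1 for a 0/6 cohort, f(6, 1) = 1 for a 1/6 cohort.

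**Results.** A simulation of 400,000 trials agreed.

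| Start | P(halt) at 6.5% | P(halt) at 30% |
|---|---|---|
| Stated in the plan | at most 5% | more than 97% |
| 38 unselected patients | 5.47% | 97.9% |
| 0/6 | 1.4% | 91.3% |
| 1/6 | 8.1% | 96.97% |
| Average given at most 1/6 | 3.4% | 95.4% |

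The first computed row reproduces the plan's 97%. It narrowly misses the 5%, which the printed table reaches at a rate of about 6.3%.

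**Averaging at 30%.** P(0/6) = 0.7^6 = 0.118 and P(1/6) = 6 × 0.3 × 0.7^5 = 0.303, total 0.420. The weights given at most 1/6 are 0.28 and 0.72, so 0.28 × 0.9133 + 0.72 × 0.9697 = 0.954. At 6.5% the weights are 0.706 and 0.294, so 0.706 × 0.0143 + 0.294 × 0.0812 = 0.034.

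**Why the unselected figure is higher.** At 30%, the permitted starts contribute 0.420 × 0.954 = 0.401 to the 0.979. The other 0.578 comes from starts with two or more DLTs, which have probability 1 − 0.420 = 0.580 and from which phase II cannot open.

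**Sensitivity.**
- No look at patient 38, when no accrual is left to halt: P(halt) at 30% is 90.1% (0/6), 96.5% (1/6) and 94.7% (average).
- The section also introduces the table this way: "Table below shows the number of DLTs allowed for a given number of “assessable” patients up to that point". If a halt needs the count to exceed the printed value, P(halt) at 6.5% / 30% is 1.1% / 94.1% (unselected), 0.2% / 81.7% (0/6) and 1.4% / 91.3% (1/6). The 97% then fails throughout, so halting on reaching the value is the reading that fits the plan's figure.
- The stopping-rule section glosses DLT more narrowly (grade 4, 30 days) than Section V.1. A narrower definition still leaves 0 or 1 DLT in the six.

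**Phase I and phase II together at 30%.** P(six-patient cohort passes and phase II never halts) = 0.420 × (1 − 0.954) = 0.019, so about 98.1% are caught at one stage or the other.

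**The case against.** The best defence is that the 97% figure is a correct unconditional operating characteristic: the section describes a boundary for 38 patients, and for 38 patients counted from zero the probability is 97.9%. That stands. A reader might infer that the figure was miscalculated, and the arithmetic does not support that. The fault is in applying it to a sequence whose first six members cannot have two or more DLTs.

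A second defence is that the phase I selection is itself a safety screen. This also stands. A reader might infer from the 0/6 result (8.7% missed against a stated ceiling of 3%) that the trial as a whole is about three times as likely to miss a 30% rate as claimed. The documents do not support that: a 0/6 cohort has probability only 11.8% at that rate, and the two phases together miss about 1.9%.

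Third, a conditional false-halt probability naturally rises once a DLT has been seen, and the average over permitted starts, 3.4%, is within the cap. That is fair, so the 8.1% does not show that the boundary was badly calibrated. It does show that the stated cap does not hold for a trial starting from 1/6.

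Finally, reaching a boundary leads to suspension of accrual and review, and Section VII provides weekly investigator review and a monitoring committee with power to suspend. This limits the consequence but does not make the stated figures apply.

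**Conclusion.** The point holds as a misstatement of the phase II rule's properties, of moderate weight. Neither permitted start delivers both stated figures. Two gaps are material: 91.3% against more than 97% at a 30% rate after 0/6, and 8.1% against at most 5% at a 6.5% rate after 1/6. They are alternatives and cannot both apply to one trial. Two others are negligible: the 0.03-point shortfall at 30% after 1/6, and the unselected 5.47% against 5%.

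The conclusion rests on independent DLTs at a constant rate, a look at every patient from 8 to 38, and a halt when the count reaches the printed value. Under the other reading of the table the numbers change but the 97% is still missed. The documents do not say whether the MTD cohort had 0 or 1 DLT, nor do they say that the rule was approved on the strength of these probabilities.

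**What to change.** Keep the table. In Section VI, Early Stopping Rule for Toxicity, state that accrual is suspended when the cumulative DLT count among assessable patients, including the six carried forward, equals or exceeds the printed value. Replace the two probability statements with conditional ones: with no DLT in the MTD cohort, a halt has probability 1.4% at a 6.5% DLT rate and 91.3% at 30%; with one DLT, 8.1% and 97.0%. If the phase I count is already known, give only the matching pair.

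The sponsor may prefer to regenerate the boundary for the 32 new patients conditional on that count. In that case the section's two benchmarks must be reconciled first, because it calibrates the false-halt probability at 6.5% but also describes DLT rates up to 20% as expected or acceptable. At 20% the printed table halts with probability 54.7% from 0/6 and 75.5% from 1/6.

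The cost is a short change of text and a written amendment, which Section VII sends to the Scientific Review Committee and the IRB. No patients are added. The stated detection probability becomes slightly less favourable.

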6. In setting of increase chronic GVHD activity upon taper, increase prednisone dose as needed, with upper limit of 1-2mg/kg/day
7. Following complete discontinuation of prednisone, begin taper of other immune suppressive agents as tolerated.

ii. Ofatumumab

Ofatumumab Administration

Ofatumumab will be administered by IV infusion, with cohort-dependent dosing in the phase I dose escalation component of this study. Following definition of the ofatumumab MTD in the phase I component, this dose will be carried forward as the recommended phase II dose.

The following dose cohorts to be tested in the phase I component:

(cohort -1): 100mg days 0 and 14

cohort 1: 300mg days 0 and 14

cohort 2: 700mg days 0 and 14

cohort 3: 1000mg days 0 and 14

****cohort/dose level -1 (100mg days 0 and 14) will be pursued only if 2/3 patients in cohort 1 (300mg days 0 and 14) experience DLT.***

The following instructions are to be followed for infusion of ofatumumab:

Pre-medication before each ofatumumab infusion must be given within 30 minutes to 2 hours prior to the treatment:

Pre-medication Requirements prior to Ofatumumab Infusions

Infusion #	Acetaminophen (po) or equivalent	Antihistamine (iv or po) diphenhydramine or equivalent	Glucocorticoid (iv)* methylprednisolone or equivalent
1 st	1000 mg	50 mg	50 mg
2 nd	1000 mg	50 mg	50 mg

*This is in addition to the daily prednisone (or equivalent) therapy

Vital sign monitoring during Ofatumumab infusion:

Vital signs will be monitored every 30 (+/- 5) minutes as standard procedure during ofatumumab infusion, or more frequently if needed based on the clinician's judgment.

First Infusion of Ofatumumab:

The initial rate of the first infusion of ofatumumab (300mg at 0.3 mg/mL; 700mg at 0.7mg/mL; and 1000mg at 1mg/mL) should be 12 mL/h. If no infusion reactions occur the infusion rate may be increased as tolerated every 30 minutes, to a maximum of 400 mL/h, according to the following table. If this schedule is followed, the infusion duration will be approximately 4.6 hours.

Infusion rate at 1st ofatumumab infusion

Time	mL/hour
0 – 30 minutes	12
31 – 60 minutes	25
61 – 90 minutes	50
91 – 120 minutes	100
121 - 150 minutes	200
151 - 180 minutes	300
181+ minutes	400

*acceptable window surrounding each time frame for escalation of infusion rate is +/- 10 minutes.

Dose Modification

- If an infusion reaction develops, the infusion should be temporarily slowed or interrupted.

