- For Grade 4 infusion reactions, do not resume the infusion (subjects who experience a grade 4 toxicity at least possibly due to ofatumumab will not receive further doses of ofatumumab).
- For Grade 1, 2, or 3 infusion reaction, if the infusion reaction resolves or remains less than or equal to Grade 2, resume infusion with the following modifications according to the initial Grade of the infusion reaction:

Grade 1 or 2: Infuse at one-half of the previous infusion rate.

Grade 3: Infuse at a rate of 12 mL/hour.

Thereafter, the infusion rate may be increased as tolerated.

Subsequent Infusions of Ofatumumab:

If the previous infusion has been completed without grade ≥ 3 infusion-associated AEs, the subsequent infusion of ofatumumab (300mg at 0.3 mg/mL; 700mg at 0.7mg/mL; and 1000mg at 1mg/mL) can start at a rate of 25 mL/hour and may be doubled approximately every 30 minutes up to a maximum of 400 mL/h, according to the following table. Duration of the infusion will be approximately 4 hours if this schedule is followed. If the previous infusion has been completed with grade ≥ 3 infusion-associated AEs, the subsequent infusion should start at a rate of 12 mL/hour. However, actual dose delivered (e.g. 300mg, 700mg or 1,000mg dose cohort level) will not be modified on day 14 dose.

Dose Modification for subsequent infusions of Ofatumumab:

- If an infusion reaction develops, the infusion should be temporarily slowed or interrupted.
- For Grade 4 infusion reactions, do not resume the infusion (subjects who experience a grade 4 toxicity at least possibly due to ofatumumab will not receive further doses of ofatumumab)
- For Grade 1, 2, or 3 infusion reaction, if the infusion reaction resolves or remains less than or equal to Grade 2, resume infusion with the following modifications according to the initial Grade of the infusion reaction:

Grade 1 or 2: Infuse at one-half of the previous infusion rate.

Grade 3: Infuse at a rate of 12 mL/hour.

Thereafter, the infusion rate may be increased as tolerated.

Infusion rate at subsequent ofatumumab infusion

Time	mL/hour
0 – 30 minutes	25
31 – 60 minutes	50
61 – 90 minutes	100
91 – 120 minutes	200
121+ minutes	400

*acceptable window surrounding each time frame for escalation of infusion rate is +/- 10 minutes.

During infusion the patient should be monitored closely and appropriate measurements should be performed whenever judged necessary.

Technical details of Ofatumumab composition and dosing:

Medication

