ofatumumab. Liver chemistries consist of ALT, AST, total bilirubin, and alkaline phosphatase. Patients will have liver function tests performed before study therapy. Study patients will have liver function tests performed at least at each study visit. Patients with elevated liver function tests due to chronic GVHD are eligible. Grade 4 hepatic toxicity attributable to ofatumumab will inform the determination of dose-limiting toxicity in the phase I component of the study. In the phase II component, ongoing monitoring of AEs will capture any grade 4 hepatic toxicity attributable to ofatumumab, and review of these AEs will ensure patient safety.

Liver interruption/stopping criteria:

- Liver chemistry stopping and follow up criteria has been designed to assure subject safety and to evaluate liver event etiology. The sponsor-investigator is to review all events which meet liver chemistry stopping criteria to determine if the event was due to:

- tumor lysis (this is not likely in this study, as relapse of primary malignancy is an exclusion criterion), disease related liver involvement, or specifically hepatic chronic GVHD
- concomitant chemotherapy (or other medications)
- other identified cause and to exclude drug induced liver injury (DILI) due to Ofatumumab

These criteria are relevant for Ofatumumab studies because transient elevations in LFTs may be due to disease related liver involvement (particularly hepatic chronic GVHD in this study) or due to other chemotherapy (or other medication insults) rather than drug induced liver injury from Ofatumumab.

If the event is determined to be due to causes other than Ofatumumab DILI and improvement is observed after withdrawal of Ofatumumab, rechallenge may be attempted if deemed appropriate by the sponsor-investigator and in addition to consent of the subject.

Oncology Ofatumumab Protocols Liver Interruption/Stopping Criteria:

1. ALT >3 times upper limit of normal (ULN) **and** bilirubin >2 times ULN (>35% direct bilirubin; bilirubin fractionation required[‡])
2. ALT >8 times ULN
3. ALT >5 times ULN for more than 2 weeks

‡ NOTE: *If serum bilirubin fractionation not immediately available, study drug should be discontinued if ALT > 3xULN and bilirubin >2xULN. Serum bilirubin fractionation should be performed if testing is available. If testing unavailable, record presence of detectable urinary bilirubin on dipstick, indicating direct bilirubin elevations and suggesting liver injury.*

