*****NOTE: These criteria hold true for patients without LFT abnormalities before initiation of therapy for chronic GVHD. Thus, in these cases, new development of LFT abnormalities following administration of the study drug would necessarily prompt this evaluation. However, for patients with established LFT abnormalities due to chronic GVHD before initiation of study therapy, these rules will be based on progression of LFT abnormalities beyond these thresholds based on the pre-therapy starting point.**

When any of the liver chemistry stopping criteria is met, do the following:

Immediately stop study treatment

Hold Ofatumumab for two weeks, repeat liver chemistry testing at least twice weekly, and report to sponsor-investigator to discuss the possibility of re-challenging with Ofatumumab. *Medication is interrupted and it is a clinical and patient decision if Ofatumumab may be re-started.*

Report SAE to Novartis within 24 hours

All events of ALT > 3xULN **and** bilirubin > 2xULN (>35% direct bilirubin) (or ALT>3xULN and INR>1.5, if INR measured; INR measurement is not required and the threshold value stated will not apply to subjects receiving anticoagulants), termed 'Hy's Law', **must be reported as an SAE (excluding studies of hepatic impairment or cirrhosis).**

NOTE: if serum bilirubin fractionation is not immediately available, study treatment should be discontinued if ALT > 3xULN **and** bilirubin > 2xULN. Serum bilirubin fractionation should be performed if testing is available. If testing is unavailable, **record presence of detectable urinary bilirubin on dipstick**, indicating direct bilirubin elevations and suggesting liver injury.

Liver chemistry follow-up assessments are to be followed until liver chemistries resolve, stabilize or return to baseline values.

Liver Chemistry Follow-up Assessments; (these chemistry tests/ assessments below are to be performed at the time of the event and then continued and/or discontinued at the discretion/judgment of the sponsor-investigator; please refer to stopping criteria within this document below)

Viral hepatitis serology including:

- *Hepatitis A IgM antibody;*
- *Hepatitis B surface antigen and Hepatitis B Core Antibody (IgM);*
- *Hepatitis C RNA;*
- *Cytomegalovirus IgM antibody;*

- *Epstein-Barr viral capsid antigen IgM antibody (or if unavailable, obtain heterophile antibody or monospot testing);*
- *Hepatitis E IgM antibody*

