Serum creatine phosphokinase (CPK) and lactate dehydrogenase (LDH)

Fractionate bilirubin, if total bilirubin >2xULN

Obtain complete blood count with differential to assess eosinophilia

Record the appearance or worsening clinical symptoms of hepatitis, or hypersensitivity, fatigue, decreased appetite, nausea, vomiting, abdominal pain, jaundice, fever, or rash

Record use of concomitant medications, acetaminophen, herbal remedies, other over the counter medications, or putative hepatotoxins

Increased alcohol use

The following assessments are required for subjects with ALT >3xULN and bilirubin >2xULN (.35% direct) but are optional for other abnormal liver chemistries:

- Anti-nuclear antibody, anti-smooth muscle antibody, and Type 1 anti-liver kidney microsomal antibodies
- Liver imaging (ultrasound, magnetic resonance, or computerized tomography) to evaluate liver disease.

Stopping Criteria:

- For subject meeting liver stopping criteria 1:
 - A repeat of liver chemistries within 24 hours, liver event follow-up assessments and close monitoring
 - A specialist or hepatology consultation is recommended
 - Monitor subjects twice weekly until liver chemistries (ALT, AST, alkaline phosphatase, bilirubin) resolve, stabilize or return to within baseline values.
- For subjects meeting criteria 2 or 3:
 - A repeat of liver chemistries within 24 to 72 hours for repeat liver chemistries and liver event follow-up assessments
 - Monitor subjects weekly until liver chemistries (ALT, AST, alkaline phosphatase, bilirubin) resolve, stabilize or return to within baseline values
- After holding Ofatumumab for two weeks:
 - If the treatment is exhibiting efficacy **and** the subject wants to continue therapy after being informed of the results of liver chemistry testing, then the Ofatumumab may be re-started.
 - Liver chemistries and follow-up assessments should be monitored at a minimum of every 2 weeks until resolution, stabilization, or a return to

baseline values, at which point monitoring should be continued per protocol

- Subjects with ALT >3xULN **but** <5xULN **and** bilirubin <2xULN without hepatitis symptoms or rash, and who may be monitored weekly for at least 4 weeks, then the following actions should be taken:
 - Subjects can continue Ofatumumab
 - Weekly repeat of liver chemistries until they resolve, stabilize, or return to baseline values, then monitor liver chemistries as per protocol assessment schedule

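### The liver-safety text gives inconsistent conditions for restarting ofatumumab after a liver stopping event, so whether a held second dose may be given depends on which paragraph is followed

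*Combined protocol and SAP*

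**What the plan says.** Four places in the combined protocol and SAP bear on re-dosing after a liver event.

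- **Section VII, Liver interruption/stopping criteria.** The sponsor-investigator reviews every stopping event for its cause. The listed causes end with "other identified cause and to exclude drug induced liver injury (DILI) due to Ofatumumab". If the event is judged "due to causes other than Ofatumumab DILI and improvement is observed after withdrawal of Ofatumumab, rechallenge may be attempted if deemed appropriate" by the sponsor-investigator, with the patient's consent as a further condition.
- **Section VII, actions when a stopping criterion is met.** Ofatumumab is held for two weeks, and the site must "report to sponsor-investigator to discuss the possibility of re-challenging with Ofatumumab". The next sentence says that "it is a clinical and patient decision if Ofatumumab may be re-started".
- **Section VII, Stopping Criteria, the item on what follows the two-week hold.** If the treatment shows efficacy and "the subject wants to continue therapy after being informed of the results of liver chemistry testing, then the Ofatumumab may be re-started". This item comes after the instructions for criterion 1 and for criteria 2 and 3, and is not limited to any of them.
- **Section IV.ii, Dose Modification.** In a parenthesis attached to the rule for grade 4 infusion reactions, "subjects who experience a grade 4 toxicity at least possibly due to ofatumumab will not receive further doses of ofatumumab".

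Two infusions are planned at every dose level, for example "cohort 1: 300mg days 0 and 14". The Study Calendar gives the treatment visits a window of 3 days either side.

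**The concern.** The three texts in section VII answer the same question with different tests. The first depends on cause and improvement, the second on discussion and discretion, the third on efficacy and the patient's wish. Nothing says which governs, or that a patient must satisfy all of them. The post-hold item is written as sufficient on its own terms and does not refer back to the causality review.

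With only two doses, the restart rule decides whether a held second dose is given. Two investigators with identical patients could act in opposite ways, each with support in the text. One of them could re-expose a patient after liver injury attributed to the study drug. Attribution will often be a real question here, because patients whose liver tests are abnormal from chronic GVHD are expressly eligible.

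**Working it through.** The plan gives no figure on this point, so the check is a comparison of texts followed by a short day count.

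**Conditions side by side**

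| Condition | Introductory paragraph (VII) | Actions on meeting a criterion (VII) | After the two-week hold (VII) |
|---|---|---|---|
| Cause other than ofatumumab | required | not stated | not stated |
| Improvement after withdrawal | required | not stated | not stated |
| Sponsor-investigator | must find it appropriate | must be told, to discuss | not stated |
| Patient | consent | shares the decision | informed and wishes to continue |
| Efficacy | not stated | not stated | required |

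**Test cases**

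1. *Event before dose 2, attributed to ofatumumab, treatment showing efficacy, patient willing.* The introductory paragraph gives no permission, because its condition on cause fails. The actions text leaves the matter to clinician and patient after the report. The post-hold item permits restart.
2. *Event before dose 2, not due to ofatumumab, improving, sponsor-investigator and patient agree, no efficacy yet.* The introductory paragraph permits rechallenge. The post-hold item's efficacy condition is not met. The disagreement runs the other way.
3. *Case 1 at grade 4.* If the parenthesis in section IV covers any toxicity, no further dose is given, while the post-hold item read alone still permits one. If it covers only infusion reactions, it has no bearing and the case reduces to case 1. The text does not settle its scope.
4. *Any event after dose 2.* No planned dose remains, so the texts cannot lead to different dosing.

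**Fit with the dosing window**

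Count days from the first infusion (an assumption; the calendar does not say how the window is anchored).

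- A two-week hold starting on day d ends on day d + 14.
- The dose 2 window closes on day 14 + 3 = 17.
- Dose 2 falls inside the window only if d + 14 ≤ 17, that is, d ≤ 3.
- The calendar schedules no liver tests between day 0 and day 14. An event found at the day 14 visit (day 11 to day 17 with the window) starts a hold that ends on day 25 (11 + 14) to day 31 (17 + 14). That is 8 (25 − 17) to 14 (31 − 17) days after the window closes.

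The restart texts do not say whether a second dose that late is allowed.

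**The case against.** The best defence reads section VII as a sequence: the sponsor-investigator reviews cause, the drug is held and the event reported, then efficacy and the patient's wish are considered after the hold. All of this sits in one continuous liver section, every restart statement is permissive, and one sponsor-investigator reviews all such events. That reading is reasonable, and central review reduces the chance of divergent practice. But the documents never say the conditions accumulate, and someone following the post-hold item alone meets no condition on cause.

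Several stronger readings are tempting and are not supported:

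- *That the protocol outright forbids a second dose after any liver injury attributed to ofatumumab.* The introductory paragraph only grants permission for other causes; it excludes drug-attributed events by implication.
- *That section IV plainly forbids what section VII allows at grade 4.* The bar sits in a parenthesis within the infusion-reaction rules. Its wording is wide enough to cover other toxicity, but its scope is unclear.
- *That every attributed liver event is affected.* Events after dose 2 are not, though liver monitoring continues for at least 6 months after the last dose. Criterion 3 requires ALT above five times the upper limit for more than two weeks, so an elevation beginning after day 0 cannot meet it by nominal day 14. Even the post-hold item requires efficacy.
- *That the MTD or the phase II toxicity boundary is compromised.* Cohort decisions and the boundary rest on patients with a DLT. A patient already counted at the first liver event is not counted again after re-dosing, and no case that changes the count has been shown.

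**Conclusion.** The point stands as an internal contradiction that must be reconciled. For an event attributed to ofatumumab and detected before dose 2, the introductory paragraph gives no permission to restart and the post-hold item gives it. For an improving event with another cause and no efficacy yet, the answers are reversed. Followed literally, the post-hold item allows re-exposure that the introductory paragraph does not permit.

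The reach is narrow: only events found before the second infusion. How many that would be cannot be estimated, because the documents give no expected frequency. The consequences shown are for patient safety and uniform dosing. No effect on alpha, power, sample size, the DLT count or the MTD is demonstrated.

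The conclusion rests on the conditions not being stated as cumulative. It does not depend on how the parenthesis in section IV is read, since the conflict within section VII exists without it.

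**What to change.** Reconcile the three section VII texts and the section IV parenthesis into one restart rule, stated once and cross-referenced elsewhere. It should say:

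- whether cause, improvement, efficacy, grade and sponsor-investigator agreement are each conditions for restart;
- whether the conditions are cumulative;
- whether the grade 4 bar in section IV extends beyond infusion reactions to liver events;
- how a two-week hold fits the day 14 window of 3 days either side, including whether a second dose may fall outside it.

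The clinical content of the rule is for the sponsor and investigator to decide; this review takes no position on it. The cost is a protocol wording amendment with the usual scientific and ethics review. The reconciliation itself adds no patients or procedures and does not alter the two-stage design.
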